| | | | DDMONYYYYTHH:MM | 0.25 | 0.XX | X | XXX.X |
| | | | DDMONYYYYTHH:MM | 0.50 | 0.XX | X | XXX.X |
| | | | DDMONYYYYTHH:MM | 1 | X | X | XXX.X |
| | | | DDMONYYYYTHH:MM | 2 | ND | | |
| | | | DDMONYYYYTHH:MM | 4 | X | -X | XXX.X |
| | | | DDMONYYYYTHH:MM | 6 | X | X | XXX.X |
| | | | DDMONYYYYTHH:MM | 8 | X | X | XXX.X |
| | | | DDMONYYYYTHH:MM | 12 | XX | -X | XXX.X |
| | | | DDMONYYYYTHH:MM | 18 | XX | X | XXX.X |
| | | | DDMONYYYYTHH:MM | 24 | XX | X | XXX.X |
| | | | DDMONYYYYTHH:MM | 30 | XX | X | XXX.X |
| | | | DDMONYYYYTHH:MM | 36 | XX | X | XXX.X |
| | | | DDMONYYYYTHH:MM | 42 | XX | -X | XXX.X |
| | | | DDMONYYYYTHH:MM | 48 | XX | X | XXX.X |
| | | | DDMONYYYYTHH:MM | 54 | XX | X | XXX.X |
| | | | DDMONYYYYTHH:MM | 60 | XX | X | XXX.X |
| | | | DDMONYYYYTHH:MM | 66 | XX | X | XXX.X |
| | | | DDMONYYYYTHH:MM | 72 | XX | -X | XXX.X |
| | | | DDMONYYYYTHH:MM | 84 | XX | X | XXX.X |
| | | | DDMONYYYYTHH:MM | 96 | XX | X | XXX.X |
| | | | DDMONYYYYTHH:MM | 168 | XX | X | XXX.X |
| | | | DDMONYYYYTHH:MM | 240 | XX | X | XXX.X |

BLQ=below limit of quantitation

ND=Not Done

Source: list SAS datasets used to create listing

DDMONYYYYTHH:MM

SAS X.Y

program_name

Note to programmer: Insert a page break after each subject. If a sample was not collected - put ND in actual column under time from dose. Sort listing within subject by sample date and time.

Pacira Pharmaceuticals
Listing 16.2-24.2: Pharmacokinetic Parameters - EXPAREL Subjects
Treatment: EXPAREL

Protocol: 402-C-329

| Site | Subject | AUC (0-inf) (ng*hr/mL) | AUC (0-last) (ng*hr/mL) | Cmax ng/mL | Tmax (hr) | Half-life (hr) | Lambda_z (hr) |
|------|----------|---------------------------|----------------------------|---------------|--------------|-------------------|------------------|
| XXX | XXX-YYYY | XXXX.XX | XXXX.XX | XXX.X | XX.X | X.XXX | X.XXX |
| | XXX-YYYY | NC | XXXX.XX | XXX.X | XX.X | NC | NC |
| | XXX-YYYY | XXXX.XX | XXXX.XX | XXX.X | XX.X | X.XXX | X.XXX |
| | XXX-YYYY | XXXX.XX | XXXX.XX | XXX.X | XX.X | X.XXX | X.XXX |
| | XXX-YYYY | XXXX.XX | XXXX.XX | XXX.X | XX.X | X.XXX | X.XXX |
| YYY | XXX-YYYY | XXXX.XX | XXXX.XX | XXX.X | XX.X | X.XXX | X.XXX |
| | XXX-YYYY | XXXX.XX | XXXX.XX | XXX.X | XX.X | X.XXX | X.XXX |
| | XXX-YYYY | XXXX.XX | XXXX.XX | XXX.X | XX.X | X.XXX | X.XXX |
| | XXX-YYYY | XXXX.XX | XXXX.XX | XXX.X | XX.X | X.XXX | X.XXX |
| | XXX-YYYY | XXXX.XX | XXXX.XX | XXX.X | XX.X | X.XXX | X.XXX |

NC=Not Calculated

Source: list SAS datasets used to create listing
SAS X.Y

DDMONYYYYTHH:MM
program_name

Note to programmer: If a parameter was not calculated - put NC in column.

Pacira Pharmaceuticals
Listing 16.2-25: Unique Adverse Events Terms and Associated Coded Terms
MedDRA Terms

(Page X of Y)

Protocol: 402-C-329

SOC

Preferred Term

Verbatim(s)

| | |
|-------|------------------------------|
| SOC1 | XXXXXXXXXXXXXXXXXXXXXXXXXXXX |
| PT1.1 | XXXXXXXXXXXXXXXXXXXXXXXXXXXX |
| | XXXXXXXXXXXXXXXXXXXXXXXXXXXX |
| | XXXXXXXXXXXXXXXXXXXXXXXXXXXX |
| PT1.2 | XXXXXXXXXXXXXXXXXXXXXXXXXXXX |
| | XXXXXXXXXXXXXXXXXXXXXXXXXXXX |
| SOC2 | |
| PT2.1 | XXXXXXXXXXXXXXXXXXXXXXXXXXXX |
| | XXXXXXXXXXXXXXXXXXXXXXXXXXXX |

Coded using MedDRA

Source: list SAS datasets used to create listing

SAS X.Y

DDMONYYYYTHH:MM
program_name

Note to programmer: Sort by SOC and preferred term in alphabetical order

| Pacira Pharmaceuticals Listing 16.2-26: Unique Medication Terms and Associated Coded Terms Who Drug Dictionary Terms | | (Page X of Y) | Protocol: 402-C-329 |
|--|--|---------------|---------------------|
| Preferred name | Verbatim(s) | | |
| ATC1 | | | |
| ACT1 | | | |
| ACT2 | | | |
| ACT3 | | | |
| ACT4 | | | |
| Preferred name | Verbatim(s) | | |
| ATC1 | | | |
| ATC1.2 | | | |
| PN1.2.1 | XXXXXXXXXXXXXXXXXXXXXXXXXXXX XXXXXXXXXXXXXXXXXXXXXXXXXXXX | | |
| PN1.2.2 | XXXXXXXXXXXXXXXXXXXXXXXXXXXX | | |
| ATC2 | | | |
| ATC2.2 | | | |
| ATC2.3 | | | |
| ATC2.4 | | | |
| PN2.2.3.4.1 | XXXXXXXXXXXXXXXXXXXXXXXXXXXX XXXXXXXXXXXXXXXXXXXXXXXXXXXX | | |

Coded using Who Drug Dictionary

Source: list SAS datasets used to create listing
SAS X.Y

DDMONYYYYTHH:MM
program_name

Note to programmer: Sort by ATC1, ATC2, ATC3, ATC4 and preferred name in alphabetical order

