Appendix 3: Postoperative Symptom Severity (PoSSe) Scale Questionnaire

Subjects will complete the PoSSe scale at 72 hours after the beginning of study drug administration and on Day 7.

PoSSe Scale

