7.6.1.8. Postoperative Symptom Severity (PoSSe) Questionnaire

The PoSSe score is the total score of the weighted responses for each question. If a response is missing to any question in the PoSSe, the total score will not be calculated.

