7.6.2.3.10. Postsurgical Symptom Severity (PoSSe) Scale Questionnaire

The total PoSSe score at 72 hours and Day 7 will be summarized (n, mean, SD, median, minimum and maximum) by treatment group. Individual question scores will be summarized (n, mean, SD, median, minimum and maximum) by treatment group at each of the assessment timepoints as well.

The total score is the sum of the individual question values (see [Listing 16.2-11.2 for values](#)). The total score will be derived only if all questions are answered.

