| | XXX-YYYY | XXX | XXX | XXX | XXX |

Pain-free is defined as an NRS score ≤ 0 at that timepoint and no prior rescue medication use.

Source: list SAS datasets used to create listing
SAS X.Y

DDMONYYYYTHH:MM
program_name

Note to programmer: Pain-free is a YES/NO value.

Pacira Pharmaceuticals
(Page X of Y)
Listing 16.2-10: Subject Satisfaction with Post-Surgical Pain Control - Randomized Subjects
Treatment: TTTTTT

Protocol: 402-C-329

| Site | Subject | Assessment | Date and Time | Rating | Score |
|------|----------|------------|-----------------|------------------------------------|-------|
| XXX | XXX-YYYY | 24 hr | DDMONYYYYTHH:MM | EXTREMELY DISSATISFIED | 1 |
| | XXX-YYYY | 48 hr | DDMONYYYYTHH:MM | DISSATISFIED | 2 |
| | XXX-YYYY | 72 hr | DDMONYYYYTHH:MM | NEITHER SATISFIED NOR DISSATISFIED | 3 |
| | XXX-YYYY | 96 hr | DDMONYYYYTHH:MM | SATISFIED | 4 |
| | XXX-YYYY | Day 10 | DDMONYYYYTHH:MM | EXTREMELY SATISFIED | 5 |
| XXX | XXX-YYYY | 24 hr | DDMONYYYYTHH:MM | XXXXXXXXXXXXXXXXXXXXXXXXXXXXXX | X |
| | XXX-YYYY | 48 hr | DDMONYYYYTHH:MM | XXXXXXXXXXXXXXXXXXXXXXXXXXXXXX | X |
| | XXX-YYYY | 72 hr | DDMONYYYYTHH:MM | XXXXXXXXXXXXXXXXXXXXXXXXXXXXXX | X |
| | XXX-YYYY | 96 hr | DDMONYYYYTHH:MM | XXXXXXXXXXXXXXXXXXXXXXXXXXXXXX | X |
| | XXX-YYYY | Day 10 | DDMONYYYYTHH:MM | XXXXXXXXXXXXXXXXXXXXXXXXXXXXXX | X |

Source: list SAS datasets used to create listing
SAS X.Y

DDMONYYYYTHH:MM
program_name

Note to programmer: Possible values for rating and score are indicated in first 5 rows of mock-up.

Pacira Pharmaceuticals

(Page X of Y)

Protocol: 402-C-329

Listing 16.2-11.1: Postoperative Symptom Severity (PoSSe) Scale Questionnaire - Randomized Subjects

Treatment: TTTTTT

| Site | Subject | Question Score (%) (see Listing 16.2-11.2 for question text & scoring) | | | | | | | | | | | | | | Total (%) |
|------|----------|--|------|------|------|------|------|------|------|------|------|------|------|------|------|-----------|
| | | 1a | 1b | 2a | 2b | 3a | 3b | 4a | 4b | 5a | 5b | 6a | 6b | 7a | 7b | |
| XXX | XXX-YYYY | X.XX | X.XX | X.XX | X.XX | X.XX | X.XX | X.XX | X.XX | X.XX | X.XX | X.XX | X.XX | X.XX | X.XX | X.XX |
| | XXX-YYYY | X.XX | X.XX | X.XX | X.XX | X.XX | X.XX | X.XX | X.XX | X.XX | X.XX | X.XX | X.XX | X.XX | X.XX | XX.XX |
| | XXX-YYYY | X.XX | NA | X.XX | NC |

NA=Not answered

NC=Not calculated

Total = sum of all scores; ranging from 0% (least severe) to 100% (most severe).

Source: list SAS datasets used to create listing

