SAS X.Y

DDMONYYYYTHH:MM

program_name

Pacira Pharmaceuticals
Listing 16.2-11.2: Postoperative Symptom Severity (PoSSe) Scale Questionnaire - Questions

(Page 1 of 2)

Protocol: 402-C-329

Eating:

- 1a. In the last week, has your operation affected your enjoyment of food?
[0]No, not at all; [5.25] Yes, a little; [10.5] Yes, very much
- 1b. In the last week, for how many days were you unable to open your mouth normally because of your operation?
[0]0 days; [2.63]1-2 days; [5.25]3-4 days; [7.88]5-6 days; [10.5] 7 days

Speech:

- 2a. In the last week, for how many days was your voice affected because of your operation?
[0]0 days; [1.25]1-2 days; [2.5]3-4 days; [3.75]5-6 days; [5] 7 days
- 2b. On the worst day of the last week, how badly was your speech affected by your operation?
[0]Not at all; [1.25]Slightly; [2.5]Moderately; [3.75]Severely; [5]Unable to speak at all

Sensation:

- 3a. Thinking of the last week, for how many days were your lips or tongue felling tingling because of your operation?
[0]None at all; [2]1-2 days; [4]3-4 days; [6]5-6 days; [8] 7 days
- 3b. Thinking of the last week, for how many days were you lips or tongue felling numb because of your operation?
[0]None at all; [2]1-2 days; [4]3-4 days; [6]5-6 days; [8] 7 days

Appearance:

- 4a. Thinking of the last wekk, for how many days were your face and/or neck bruised because of your operation?
[0]None at all; [1.5]1-2 days; [3]3-4 days; [4.5]5-6 days; [6] 7 days
- 4b. Thinking of the last week, for how many days were your face and/or neck swollen because of you operation?
[0]None at all; [1.5]1-2 days; [3]3-4 days; [4.5]5-6 days; [6] 7 days

Source: list SAS datasets used to create listing
SAS X.Y

DDMONYYYYTHH:MM
program_name

Pacira Pharmaceuticals (Page 2 of 2) Protocol: 402-C-329
Listing 16.2-11.2: Postoperative Symptom Severity (PoSSe) Scale Questionnaire - Questions

Pain:

5a. Thinking of the last week, for how many days did you experience pain from your operation?
[0]None at all; [2.38]1-2 days; [4.75]3-4 days; [7.13]5-6 days; [9.5] 7 days

5b. Thinking of the last week, has the pain from your operation been controlled by pain killers?
[0] I have had no pain; [2.38] Yes, completely controlled;
[4.75] Controlled mostly but still some discomfort; [7.13] Poorly controlled;
[9.5] Not controlled at all

Sickness:

6a. Thinking of the last week, for how many days did you vomit or feel nauseated?
[0]None at all; [1.25]1-2 days; [2.5]3-4 days; [3.75]5-6 days; [5] 7 days

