6b. On the worse day of the last week, how many times did you vomit or feel nauseated?
[0]None at all; [1.25]One day; [2.5]2-3 times; [3.75]More than 3 times;
[5]All the time (all day long)

Interference with daily activities:

7a. In the last week, did the operation prevent you from carrying out work/housework and other daily activities?
[0]None at all; [0.83]I could continue with my work, but my work suffered; [1.65]Yes, for 1 day;
[2.48]Yes, for 2-6 days; [3.3]Yes, for 7 days

7b. In the last week, have your leisure activities been affected by your operation? (including sports, hobbies and social life)
[0]Not affected by the operation; [0.83]Mildly affected by the operation;
[1.65]Moderately affected by the operation; [2.48]Severely affected by the operation;
[3.3]The operation prevented any social life at all

7c. Thinking of the last week, how badly did the pain affect your life?
[0]Not at all; [1.1]Slightly; [2.2]Moderately; [3.3]Severely

Source: list SAS datasets used to create listing
SAS X.Y

DDMONYYYYTHH:MM
program_name

Pacira Pharmaceuticals
(Page X of Y)
Listing 16.2-12: Day 30 Phone Contact - Pain-Related Calls/Visits - Randomized Subjects
Treatment: TTTTTTT

Protocol: 402-C-329

| Site | Subject | Date | Visit | Number of pain-related | | |
|------|----------|-----------|--------|------------------------|---------------|-------|
| | | | | Phone calls | Office Visits | Total |
| XXX | XXX-YYYY | DDMONYYYY | Day 7 | XX | XX | |
| | XXX-YYYY | DDMONYYYY | Day 10 | XX | XX | |
| | XXX-YYYY | DDMONYYYY | Day 30 | XX | XX | XXX |

Source: list SAS datasets used to create listing
SAS X.Y

DDMONYYYYTHH:MM
program_name

Pacira Pharmaceuticals
Listing 16.2-13: Neurological Assessment - Randomized Subjects
Treatment: TTTTTTT

Protocol: 402-C-329

| Site | Subject | Assessment | Date and Time Of Assessment | | | Time From Dose | | | Questions | | | | | |
|------|----------|-----------------|-----------------------------------|----------------|---------------------|----------------|-----|-----|-----------|-----|-----|--|--|--|
| | | | Scheduled (hr) | Actual (hr) | Deviation (mins) | 1 | 2 | 3 | 4 | 5 | 6 | | | |
| XXX | XXX-YYYY | DDMONYYYYTHH:MM | 0 | XX | X | XX | XXX | XXX | XXX | XXX | XXX | | | |
| | | DDMONYYYYTHH:MM | 0.25 | 0.XX | X | XX | XXX | XXX | XXX | XXX | XXX | | | |
| | | DDMONYYYYTHH:MM | 0.50 | 0.XX | X | XX | XXX | XXX | XXX | XXX | XXX | | | |
| | | DDMONYYYYTHH:MM | 1 | X | X | XX | XXX | XXX | XXX | XXX | XXX | | | |

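### The PoSSe item weights in the SAP add up to at most 97.9, but the SAP says the total runs to 100%, so a weight or the stated range is wrong

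*SAP*

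**What the plan says.** The PoSSe mean total score is a tertiary efficacy endpoint (Protocol Section 12.2; SAP Section 7.6.1.3). The SAP defines the total in three places:

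- Section 7.6.1.8: "The PoSSe score is the total score of the weighted responses for each question".
- Section 7.6.2.3.10: "The total score is the sum of the individual question values", with a pointer to Listing 16.2-11.2 for the values.
- Listing 16.2-11.1, footnote: "Total = sum of all scores; ranging from 0% (least severe) to 100% (most severe".

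Listing 16.2-11.2 prints the value of every answer. Examples are "0]No, not at all; [5.25] Yes, a little; [10.5] Yes, very much" for item 1a, "0]0 days; [2.63]1-2 days; [5.25]3-4 days; [7.88]5-6 days; [10.5] 7 days" for item 1b and "0]Not at all; [1.1]Slightly; [2.2]Moderately; [3.3]Severely" for item 7c.

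On timing, Protocol Appendix 3 says: "Subjects will complete the PoSSe scale at 72 hours after the beginning of study drug administration and on Day 7". Most items ask about the past week, and the day-count options run up to 7 days at both visits.

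**The concern.** A total that is a plain sum, with a stated range of 0% to 100%, needs item maxima that add to 100. They do not. The SAP therefore contradicts itself on how a named endpoint is scored or on how it is labelled.

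The consequence depends on which side is wrong. If only the range is wrong, the totals are computed as intended, and readers are told that the scale ends 2.1 points higher than it does. If a weight is wrong, each total with a non-zero answer to that item is wrong. The error would carry into Table 14.2-12.1, the subject listing and the per-protocol repeats in the SAP addendum.

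A second, smaller matter is how totals are read across visits. A form that looks back a week, given 72 hours after dosing, covers fewer postoperative days than the same form given on Day 7.

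**Working it through.** **1. Sum of the maxima.** Each input is the highest printed value of an item in SAP Listing 16.2-11.2.

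| Domain | Items and maximum | Sum |
|---|---|---|
| Eating | 1a 10.5, 1b 10.5 | 21.0 |
| Speech | 2a 5, 2b 5 | 10 |
| Sensation | 3a 8, 3b 8 | 16 |
| Appearance | 4a 6, 4b 6 | 12 |
| Pain | 5a 9.5, 5b 9.5 | 19.0 |
| Sickness | 6a 5, 6b 5 | 10 |
| Daily activities | 7a 3.3, 7b 3.3, 7c 3.3 | 9.9 |

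Total = 21 + 10 + 16 + 12 + 19 + 10 + 9.9 = 97.9. The stated 100 is not reproduced; the gap is 100 − 97.9 = 2.1.

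**2. Could rounding explain it?** If each of the 15 maxima is exact to one decimal, the sum can be off by at most 15 × 0.05 = 0.75, which is less than 2.1.

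**3. Could another rule explain it?** Sections 7.6.1.8 and 7.6.2.3.10 and the listing footnote describe addition only. No division by the maximum or other rescaling appears. Leaving out item 7c, which has no column in Listing 16.2-11.1 as extracted, gives 97.9 − 3.3 = 94.6, further from 100. That missing column may come from PDF extraction, so I make nothing of it.

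**4. Attainable total at 72 hours.** Dosing day is Day 1 (Protocol Section 13.1), so 72 hours falls on Day 4. Assume that answers reflect time since surgery. Then the eight day-count items can reach 3-4 days, and item 7a can reach 2-6 days.

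- Day-count items (1b, 2a, 3a, 3b, 4a, 4b, 5a, 6a): 5.25 + 2.5 + 4 + 4 + 3 + 3 + 4.75 + 2.5 = 29.00.
- Item 7a: 2.48.
- Other items at their maximum (1a, 2b, 5b, 6b, 7b, 7c): 10.5 + 5 + 9.5 + 5 + 3.3 + 3.3 = 36.60.
- Total: 29.00 + 2.48 + 36.60 = 68.08.

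Item 6a asks about nausea or vomiting from any cause, so it need not be limited by the date of surgery. With 6a at its maximum, the total is 68.08 + (5 − 2.5) = 70.58. The range is thus about 68 to 71.

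**5. Attainable total on Day 7.** If seven days can be reported, it is 97.9. If only 5-6 days can (elapsed days counted, or an early visit within the ±1 day window), the day-count items give 7.88 + 3.75 + 6 + 6 + 4.5 + 4.5 + 7.13 + 3.75 = 43.51. The total is then 43.51 + 2.48 + 36.60 = 82.59.

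**The case against.** **The endpoint carries little weight.** PoSSe is tertiary, SAP Section 7.6.2.3 plans no test on it, and totals are summarised by arm at each visit with no change score. This stands, and it is why the point is minor. It does not remove the contradiction, which should be settled before totals are computed.

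**Daily activities must be the faulty domain.** A reader might infer this, because it is the only domain whose maximum is not a whole number: 12 would complete 100, and it has 9.9. The documents do not support the inference. It assumes that the other six domains are right, and no passage shows that. The domain is also internally consistent with a maximum of 3.3: items 7a and 7b step in quarters (0.83, 1.65, 2.48, 3.3) and item 7c in thirds (1.1, 2.2, 3.3). With a maximum of 4 per item, all eleven non-zero values would be wrong, so no single misprint accounts for it. The shortfall could lie in any domain, or only in the range label.

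**The two visits are on different scales, which distorts the results.** A reader might infer this from the lower attainable total at 72 hours. Items and weights are the same at both visits, and the form blocks no answer at 72 hours, so the limit is inferred from time since surgery. Both arms share it at each visit, so the comparison between arms at a visit is not affected. What stands is narrower: the level of a 72-hour total should not be read against the level of a later one.

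**Conclusion.** The inconsistency is real and exact: the printed weights allow at most 97.9, against a stated 100%, and neither rounding nor any defined rule closes the 2.1-point gap. Either at least one weight or the stated range is wrong. Which it is, and which item or domain, cannot be settled from the protocol and SAP.

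It would go too far to say that all totals will be wrong. If the weights are right, none is, and a wrong range label does not bias the treatment comparison. If a weight is wrong, the affected totals are those with a non-zero answer to that item, and the difference between arms could shift slightly.

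The 72-hour figure of about 68 to 71 rests on the assumption that answers reflect time since surgery. It is a matter of interpretation, not a scoring error.

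Overall this is a minor point on a descriptive tertiary endpoint.

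**What to change.** Before totals are computed, check the weights of all 15 items in SAP Listing 16.2-11.2 against the instrument's scoring key. Correct any that are wrong. If all are right, change the footnote of Listing 16.2-11.1 to a range of 0 to 97.9.

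Optionally, add a footnote to Table 14.2-12.1. It would say that recall at 72 hours covers only about 3 to 4 postoperative days, that the attainable total there is about 68 to 71 on that assumption and with the present weights, and that total levels at the two visits are not directly comparable. The shells for Tables 14.2-12.1 and 14.2-12.2 name the second visit as Day 10, while SAP Section 7.6.2.3.10 and the protocol say Day 7; align them in the same edit.

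The cost is one check against the key and a few words in the SAP. No data collection changes.

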12.3. Pharmacokinetic Analysis

Blood samples for PK analysis will be obtained at baseline (prior to study drug administration); 15 minutes, 30 minutes, 1, 2, 4, 8, 12, 18, 24, 30, 36, 42, 48, 54, 60, 66, 72, 84, and 96 hours after the beginning of study drug administration; and on Days 7 and 10. Blood samples will be collected from all subjects in order to maintain the treatment double-blind.

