13.1. Instructions for Conducting Procedures and Measures

All safety, efficacy, and PK assessments conducted after baseline will be timed from the *beginning of study drug administration*.

At timepoints when multiple assessments coincide, the NRS pain intensity assessments will be conducted first, if applicable.

Day 1 is defined as the day on which study drug is administered. The beginning of surgery is defined as the time of the first incision. The end of surgery is defined as the time of the last suture. Postsurgical is defined as after the end of surgery.

Subjects will remain in the research facility for 96 hours after study drug administration; therefore, postsurgical analgesia and collection of study data through the primary endpoint will take place under the supervision of study staff.

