5. DEFINITIONS

Study Day

Study Day is calculated as the date of event minus the date of surgery plus one (1), if the date of event is on or after the date of surgery, thus day of surgery is Day 1. Study Day is based on the calendar dates, thus days before the date of surgery have negative values while those on or after the date of surgery are positive. However for those events that have times associated with them, if the event occurs on the day of surgery but before time 0, Study Day will be -1; Study Day will be 1 for those events occurring on the day of surgery but start after time 0.

Treatment-emergent Adverse Event

Treatment-emergent adverse events (TEAEs) are those with onset between the start datetime of study drug administration and end of study (Study Day 30 ± 3 days).

Time 0 (zero)

Time 0 is defined as the date and time of the end of surgery for all end points except AEs and bupivacaine plasma concentrations. For AEs and PK sampling times 0 is defined as the date and time of the start of study drug administration.

Pain-free

Pain-free is defined as a NRS score of 0 or 1 with no rescue medication use prior to that assessment.

Time Periods

All schedule times have a window associated with them (see [Time and Events Schedule for individual timepoint windows](#)). Various time frames are used in the data analyses which are dependent on these windows. The table below defines the actual elapsed times with allowance for the windows that can be included in the window.

| Defined time frame (hrs) | Acceptable elapsed times (hrs) |
|--------------------------|--------------------------------|
| 0-24 | [0 to 25] |
| 0-48 | [0 to 50] |
| 0-72 | [0 to 76] |
| 0-96 | [0 to 100] |
| 0-Day 10 | [0 to 264] |
| 24-48 | [23 to 50] |
| 48-96 | [46 to 100] |

If there are two or more data points that fit the time window the data point that occurs the latest in the window should be used. For example when selecting the data point for the 48 hour timepoint, if a subject has data points collected at 47 and 49 hours then the 49 hour timepoint should be used. In this example the 49 hour timepoint record will be used as the end and start of all time intervals, thus the 0-48 hour interval will end using the 49 hour record and the 48-72 hour interval will start using the same 49 hour record.

Topline Result Tables

Topline result tables are to be expedited for Pacira review after database lock. The topline tables for this study are:

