7.8. Pharmacokinetic Analysis

7.8.1. Pharmacokinetic Parameter Calculation Methods

Pharmacokinetic parameters will be calculated by noncompartmental analysis method from concentration-time data following these guidelines:

- Actual sampling times relative to study drug administration will be used for all calculations of the PK parameters. If there is any doubt as to the actual time a sample was taken, then the scheduled time will be used. Descriptive statistics will be used to summarize the PK parameters.
- There will be no imputation of missing data.

For the calculation of AUCs from bupivacaine plasma concentrations, concentrations below the limit of quantification (BLOQ) will be handled as follows:

- Pre-dose values will be set to zero.
- All remaining BLOQ values will be set to missing.

Pharmacokinetic parameters will be estimated according to the following guidelines:

- The maximum observed plasma concentration (C_{max}) will be obtained directly from the concentration-time data.
- Time to maximum concentration (T_{max}) is the time at which C_{max} is observed.
- The apparent terminal elimination rate constant (λ_Z) will be estimated at terminal phase by linear regression after log-transformation of the concentrations:
 - Only those data points that are judged to describe the terminal log-linear decline will be used in the regression.

- A minimum number of three data points in the terminal phase will be used in calculating λ_z with the line of regression starting at any post- C_{max} data point (C_{max} should not be part of the regression slope) and including C_{last} , t_{last} .
- The adjusted correlation coefficient (R^2 adjusted) in general should be greater than 0.90. Any value less than 0.90 may be used at the pharmacokineticist's best knowledge and judgment.
- An appropriate number of decimal places should be used for λ_z to enable the reported value of half-life ($t_{1/2}$) to be calculated.
- Half-life ($t_{1/2}$) will be calculated as $\ln(2)/\lambda_z$.
- AUC will be calculated as follows:
 - The linear trapezoidal method will be employed for all incremental trapezoids arising from increasing concentrations and the logarithmic trapezoidal method will be used for those arising from decreasing concentrations.
 - $AUC_{(0-t)} = \int_0^t C(t)dt$
 - $AUC_{(0-\infty)} = \int_0^t C(t)dt + \int_t^{\infty} C(t)dt = AUC_{(0-t)} + C_{(t)}/\lambda_z$
 - $C_{(t)}$ is last observed quantifiable concentration.

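### The SAP listings schedule the Day 7 and Day 10 samples at 168 h and 240 h, but with dosing on Day 1 the nominal times are 144 h and 216 h

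*SAP*

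**What the plan says.** Protocol 13.1 fixes the day count: "Day 1 is defined as the day on which study drug is administered". SAP Section 5 uses the same count: "Study Day is calculated as the date of event minus the date of surgery plus one (1"). For PK, SAP Section 5 starts the clock at dosing: "For AEs and PK sampling times 0 is defined as the date and time of the start of study drug administration".

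Protocol 12.3 places the late samples at "72, 84, and 96 hours after the beginning of study drug administration; and on Days 7 and 10". Protocol Table 1 and SAP Section 10 give Days 7 and 10 a window of ±1 day.

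In SAP Section 11.2, Listing 16.2-24.1 shows the scheduled hour, actual hour and deviation in minutes for each sample. Its two rows after 96 h are "DDMONYYYYTHH:MM | 168 | XX | X | XXX.X" and "DDMONYYYYTHH:MM | 240 | XX | X | XXX.X". The same hours appear elsewhere:

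- ECG Listings 16.2-14.1 and 16.2-14.2.1 have both 168 h and 240 h.
- Neurological Listing 16.2-13 and ECG Listing 16.2-14.2.2 have 240 h only.

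SAP Section 5 also sets a time frame of "0-Day 10 | [0 to 264"].

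SAP 7.8.1 and Protocol 15.6.4 calculate PK parameters from actual sampling times, with one exception: "If there is any doubt as to the actual time a sample was taken, then the scheduled time will be used".

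**The concern.** The listed hours fit a count in which dosing is Day 0, and neither document uses that count. The scheduled hour has up to three uses. It is the reference for the deviation column. It is the value substituted when an actual sampling time is in doubt. It may also be the x-axis position in the mean PK plots of the SAP addendum (Section 3), which are built from the summary by scheduled timepoint. Characterising PK is a stated secondary objective, and where the Day 7 and Day 10 samples are quantifiable they anchor the terminal slope. A 24 h error in their fallback time therefore goes into the elimination rate constant, half-life and AUC of any subject for whom the fallback is used.

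**Working it through.** **1. Reproducing the listed hours.** 7 x 24 = 168 and 10 x 24 = 240. This works only if Day d means d x 24 h after dosing, that is, if dosing is Day 0.

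**2. Applying the documents' own rule.** With dosing on Day 1, Day d is nominally (d - 1) x 24 h after dosing.

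| Visit | Rule | Nominal | Listed | Difference | ±1 day window |
|---|---|---|---|---|---|
| Day 7 | 6 x 24 | 144 h | 168 h | 24 h | 120 to 168 h |
| Day 10 | 9 x 24 | 216 h | 240 h | 24 h | 192 to 240 h |

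Cross-check: 96 h is Study Day 96/24 + 1 = 5, so Day 7 is two days (48 h) later, at 144 h. The listing makes it three days (72 h). By the SAP's date rule, 168 h after dosing falls on Study Day 8 and 240 h on Study Day 11. The listed hours therefore lie at the upper edge of the window, not at its centre.

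**3. Deviation column** (taking deviation as actual minus scheduled). A sample at exactly 144 h shows 144 - 168 = -24 h = -1,440 min. A sample at exactly 216 h shows the same. Study Day counts dates, so the exact figure moves with clock time. After dosing at noon, Day 7 runs from 132 to 156 h, and its deviations run from -2,160 to -720 min.

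**4. Half-life under the fallback.** Assume log C = a - kt at true times t, quantifiable late samples, and a regression on listed times s. The fitted slope is -k x Sst/Sss, where Sss is the sum of squares of s and Sst the sum of cross-products of s and t. The half-life ratio is Sss/Sst, which does not depend on k.

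| Points in fit (every Day 7 or Day 10 time at its listed hour) | Sss | Sst | Ratio |
|---|---|---|---|
| 96 h, Day 7, Day 10 | 10,368 | 8,640 | 1.20 |
| 84 h, 96 h, Day 7 | 4,128 | 2,880 | 1.43 |
| 84 h, 96 h, Day 7, Day 10 | 15,660 | 12,924 | 1.21 |
| 72 h, 84 h, 96 h, Day 7 | 5,580 | 4,068 | 1.37 |
| 72 h, 84 h, 96 h, Day 7, Day 10 | 20,160 | 16,704 | 1.21 |

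If only one of the two times is in doubt (fit on 96 h, Day 7, Day 10):

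- Only Day 10 in doubt: s = 96, 144, 240; ratio 10,752/8,832 = 1.22.
- Only Day 7 in doubt: s = 96, 168, 216; ratio 7,296/7,104 = 1.03.

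**5. AUC under the fallback.** SAP 7.8.1 uses the logarithmic trapezoid for declining concentrations: area = (C1 - C2) x Δt / ln(C1/C2). Only Δt changes.

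- 96 h to Day 7: 72/48 = 1.50.
- Day 7 to Day 10, both at listed hours: (240 - 168)/(216 - 144) = 72/72 = 1.00.

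The documents give no half-life. Assuming 12 to 48 h and a fit from 72 h, AUC from 72 h to infinity is about 12% to 31% too large with Day 7 alone, and about 12% to 20% with Day 7 and Day 10.

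**6. What does not change.** Scheduled times through 96 h are right. With undoubted actual times the error is zero. Individual concentration plots use actual times (SAP 7.8.2). Table 14.2-15.1.1 in the addendum labels its last rows Day 7 and Day 10, so its statistics are the same whatever hour is attached to them.

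**The case against.** The strongest reply is that these are mock-up listings and the analysis is protected. PK parameters use actual times, and the listing records sampling to the minute. The documents do not say how often a time would be in doubt. The larger ratios need particular sets of points, and those with both late samples need both times of the same subject to be in doubt. They also need quantifiable concentrations, whereas SAP 7.8.1 sets post-dose values below the limit of quantification to missing. The 50% concerns one tail segment, and its share of total AUC is unknown. The mean plots come from a table labelled by Day and no plotting hour is given, so a stretched tail in them is only a possibility. All of this stands, and it limits the point to a minor one.

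It does not remove the error. The scheduled and deviation columns are wrong for these two timepoints however well times are recorded. The fallback is a written rule, and the only hours the SAP offers it for these samples are 168 and 240.

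A reader might also take the 264 h limit of the 0-Day 10 frame as proof of the same mistake, since 240 + 24 = 264, and want it cut to 216 + 24 = 240 h. The documents do not settle that. 264 h is also 11 x 24, which covers all of calendar Day 11. Under the date rule, a Day 11 visit at 15:00 after a 09:00 end of surgery is in window at 246 h, and a 240 h limit would drop it.

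**Conclusion.** The listed 168 h and 240 h contradict the Day 1 rule in both documents; the nominal times are 144 h and 216 h. The error is exactly 24 h and affects only these two timepoints. It makes the scheduled and deviation columns wrong, and any PK parameter for which the scheduled time replaces a doubtful actual time. In that case half-life is about 20% to 43% too long in the worked examples where every late sample in the fit carries its listed hour. It is about 3% too long if only Day 7 is in doubt and Day 10 is correct (fit on 96 h, Day 7, Day 10). The 96 h-to-Day 7 AUC segment is 50% too large whenever Day 7 takes its listed hour. These sizes assume log-linear decline and quantifiable late samples.

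A reader might infer that all nominal-time PK results in the terminal phase are 24 h late. The documents do not support that: the 72, 84 and 96 h times are correct, parameters rest on actual times unless these are in doubt, and the nominal-time table is labelled by Day. Mean plots are affected only if Day 7 and Day 10 are placed at 168 h and 240 h. Severity: minor.

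**What to change.** 1. In Listing 16.2-24.1, set the Day 7 row to 144 h and the Day 10 row to 216 h.
2. In Listings 16.2-13, 16.2-14.1, 16.2-14.2.1 and 16.2-14.2.2, set the Day 10 row to 216 h.
3. Reconcile the 168 h rows of ECG Listings 16.2-14.1 and 16.2-14.2.1 with the schedule. Protocol 12.5 and 13.6 list no Day 7 ECG, so changing the hour would leave a row with no planned assessment. Listings 16.2-13 and 16.2-14.2.2 have no Day 7 row to change.
4. State in SAP 7.8 that 144 h and 216 h are the nominal hours for deviations, for the fallback and for mean concentration plots.
5. Reconcile the 0-Day 10 frame with the Day 1 convention and the calendar-day window, and say which elapsed times it is meant to admit, instead of simply cutting it to 240 h.

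The cost is edits to shells, programs and a few lines of SAP text. Data collection does not change.
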